### 1.2 Study Rationale

Among patients with complex or monosomy karyotypes, nearly 60% carry *TP53* mutations; whereas nearly all patients with *TP53* mutations have complex or monosomy karyotypes, and these karyotypes almost always involve deletion of chromosome 5q, chromosome 7, chromosome 12, or chromosome 17p. Patients with *TP53* mutations tend to be older (median age 61 vs 54 years), have worse response to conventional chemotherapy (complete remission rate: 28% vs 50%), shorter event free survival (3-year EFS: 1% vs 13%), and overall survival (3-year OS: 3% vs 28%).

We correlated response to decitabine with mutation status in 99 patients with AML or MDS. We observed response (complete remission (CR), complete remission with incomplete blood count recovery (CRi), or marrow complete remission (mCR) in 21/21 patients with *TP53* mutations. ( $p < 0.0001$ ). No other gene mutation was associated with

response in the 99 patients sequenced (Figure 1A).

Consistent with this, we observed mutation clearance in all 16 cases with TP53 mutations evaluated at serial time points, and that TP53 mutations were cleared more quickly and consistently than other variants (Figure 2).

Decitabine alone does not lead to a cure in the majority of responding patients. Mutation clearance is nearly always incomplete, and we could detect low levels of mutations (0.2 - 5%) in 20 of 20 patients analyzed during remission with enhanced exome sequencing. Furthermore, in all 9 patients analyzed at relapse, the relapse occurred via subclonal evolution (expansion of a subclone that carries the founding clone mutations and additional mutations, suggesting that the founding clone mutations persisted during morphologic remission).

Several clinical variables correlated with survival in this cohort: age, performance status (2 vs 0-1), and whether the patient underwent stem cell transplantation (Figure 3A). Thus, additional consolidation (e.g. hematopoietic cell transplantation) appears necessary to

achieve prolonged remissions. Importantly, in this cohort of patients who undergo decitabine induction, the presence of *TP53* mutations no longer adversely affected survival following transplantation.

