### 2.2 Secondary Endpoints

1. To determine the proportion of responding *TP53* mutated patients (CR, CRi) compared to historical controls (10%-15%)
2. To determine the time to stem cell transplant among subjects who are suitable candidates for transplant and have an identified donor.
3. To correlate response and survival with clinical parameters:
  - morphologically evident disease (>5% blasts by cytomorphology) versus molecularly detected disease at the time of enrollment (disease detected with flow cytometry, cytogenetic, or mutational analysis if ≤ 5% blasts by cytomorphology);
  - *de novo AML versus secondary AML versus treatment-related AML*,
  - presence *versus* absence of cytogenetic abnormalities in addition to *TP53* mutations.
4. To determine the median time to leukemia relapse (TTLR) in non-transplant patients treated with decitabine compared to historical control (6-8 months).
5. To determine the 2-year event free survival after transplant in patients treated with decitabine compared to historical control (18-22%).
6. To determine the median and average number of hospital days during Cycles 1 and 2.

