## **E. Secondary Clinical Endpoints Analyses**

The principal measurement of toxicity will be a measure of the total number hospitalized days during the first 60 days of therapy.

**CRc rate** will be analyzed based on the ITT population. The remission rate and its 2-sided 90% confidence interval (CI) will be summarized.

**Event-free survival:** EFS will be analyzed using Kaplan-Meier methodology and Kaplan-Meier plots will be provided using the ITT analysis set. The median EFS and its 2-sided 90% CI using the complementary log-log transformation method (Collett 1994) will be calculated.

**Leukemia-free survival:** LFS will be analyzed using Kaplan-Meier methodology

and Kaplan-Meier plots will be provided using the ITT analysis set. The median LFS and its 2-sided 90% CI using the complementary log-log transformation method (Collett 1994) will be calculated.

**Time to leukemia relapse:** TTCR will be summarized using descriptive statistics.

The time to stem cell transplant, the proportion of patients who are able to undergo transplantation, and the average number of hospital days during cycles 1 and 2, will also be documented. The association between response and clinical characteristics (morphologically evident disease -i.e., >5% blasts by cytomorphology- versus molecularly detected disease at the time of enrollment -i.e., disease detected with flow cytometry, cytogenetic, or mutational analysis with  $\leq 5\%$  blasts by cytomorphology-, *de novo AML versus secondary AML versus treatment-related AML*, presence *versus* absence of cytogenetic abnormalities in addition to *TP53* mutations, etc.) will be described using contingency tables and compared by Chi-square test or Fisher's exact test as appropriate. The association between survival (OS, EFS, LFS) and clinical characteristics will be described using Kaplan-Meier methods and compared by log-rank test.

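### Objective 3 compares non-randomised disease groups one factor at a time, with no adjusted analysis for age and performance status, and its cytogenetic contrast may have very few patients on one side

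*Combined protocol and SAP*

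**What the plan says.** Section 2.2, objective 3, is "To correlate response and survival with clinical parameters". It lists three contrasts: morphologically evident versus molecularly detected disease at enrollment; de novo versus secondary versus treatment-related AML; and "presence *versus* absence of cytogenetic abnormalities in addition to *TP53* mutations".

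The only analysis of this objective is in section 15.4.E. For response, the associations "will be described using contingency tables and compared by Chi-square test or Fisher's exact test as appropriate". For survival (OS, EFS and LFS), they "will be described using Kaplan-Meier methods and compared by log-rank test". Section 15 contains no Cox or logistic model, no stratified log-rank test and no covariate adjustment. The list of characteristics in 15.4.E ends with an open-ended etc., which could add factors, but only as further single-factor comparisons.

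On prognosis, section 1.1 lists age and performance status among known markers. Section 1.2 reports of the earlier decitabine cohort: "Several clinical variables correlated with survival in this cohort: age, performance status (2 vs 0-1", and then adds stem cell transplantation. Section 3.1 admits adults of any age from 18 and performance status up to 3.

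On karyotype, section 1.2 says of nearly all patients with TP53 mutations that these "mutations have complex or monosomy karyotypes, and these karyotypes almost always involve deletion of chromosome 5q" or one of a few other chromosomal sites.

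**The concern.** The disease groups in objective 3 form themselves, and nothing in the design balances age or performance status between them. Patients with overt relapse could plausibly be frailer than those enrolled on molecular evidence alone, and patients with treatment-related AML could be older than those with de novo disease. A log-rank or Fisher test then compares mixtures of patients, and the plan offers no second analysis to show how much of a difference goes with the disease feature itself.

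The cytogenetic contrast has a separate difficulty. If almost every patient has an abnormality, the comparison group may be too small for a test to say anything, and a non-significant result could be misread as no association.

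At stake is how a secondary, correlative objective is interpreted. The primary comparison of 1-year OS with 25% does not depend on it.

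**Working it through.** The documents state no power, alpha or sample size for objective 3, so there is no figure to reproduce. Two-sided alpha 0.05 is assumed.

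**Expected deaths.** Inputs: 60 patients and 24 months' accrual (15.1); exponential survival, one further year of follow-up and 1-year OS of 40% under the alternative (15.4.G). Uniform accrual is assumed, so follow-up u is uniform on 1 to 3 years. The mean of 0.4^u is (0.4 − 0.064) / (2 × 0.9163) = 0.183, giving 60 × (1 − 0.183) = 49 deaths.

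**Effect of imbalance.** Trials of 60 patients were simulated with censoring uniform over 1-3 years. The tested factor has no effect once performance status is given. The prevalences, hazard ratios and group splits (40 vs 20 in rows 1 and 3; about 40% vs 60% in the others) are assumptions with no source in the documents.

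| Poor performance status, group A vs B | Its hazard ratio | Unadjusted rejection | Adjusted rejection |
|---|---|---|---|
| 50% vs 20% | 2 | 9% | 5.6% |
| 60% vs 30% | 2 | 11-12% | 5.4% |
| 60% vs 20% | 2.5 | 16.5% | 4.6% |
| 70% vs 20% | 2 | 22-23% | 5.8% |
| 30% vs 30% | 1.5-2.5 | 5-6% | not tabulated |

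In rows 1 and 3 the unadjusted hazard ratio averages 1.21 and 1.39; the adjusted one averages 0.99 in both. Repeat runs of these two rows agree to about one percentage point. The harshest combination tried, 70% vs 20% with hazard ratio 2.5, gave 33% unadjusted. A milder hazard ratio of 1.5 gave 7% (60% vs 30%) and 11% (70% vs 20%).

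**Room for adjustment in OS.** Age, performance status and one binary factor use three parameters: 49/3 = 16 deaths each. With three-level AML type there are four: 49/4 = 12. All six together leave 49/6 = 8.

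**Cytogenetic contrast.** Log-rank power is Φ(√(d·p·(1 − p)) × ln HR − 1.96), with d = 49 and p the share without an abnormality. Section 1.2 gives no percentage, so p is varied. Example, 3 of 60: √(49 × 0.05 × 0.95) = 1.526; 1.526 × 0.693 − 1.96 = −0.90; power 18%.

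| Patients without abnormality | Power for HR 2 |
|---|---|
| about 2 (3%) | 13% |
| 3 | 18% |
| 6 | 31% |
| 10 | 44% |
| 15 | 56% |
| 30 (even split) | 68% |

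For 80% power the hazard ratio would have to be about 6.3 with 3 such patients and 3.8 with 6.

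For response, take two patients without an abnormality and 20 responders among 60. The smallest attainable Fisher p is (20 × 19)/(60 × 59) = 0.11. With 30 responders it is 2 × (30 × 29)/(60 × 59) = 0.49. Neither case can reach 0.05.

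**The case against.** The strongest reply is that the tests fit the objective as written. It asks for correlations, 15.4.E says associations will be described, and no decision follows from them. An unadjusted log-rank test answers a marginal question. When performance status differs between groups, their survival curves really do differ, so the 9-23% are errors only against a conditional null that the plan never states. This stands. A reader might infer that the type I error of the planned tests is inflated, or that the group differences will be confounded. The documents support neither: they give no imbalance, and without one the unadjusted test behaves.

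Performance status may also be partly a consequence of disease burden, in which case adjustment removes some of the association of interest. This stands too, and argues for showing both results. Section 1.2 reports a correlation with survival, not a cause. Transplantation, named in the same sentence, happens after baseline and would need time-dependent handling.

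On karyotype, a reader might infer that the contrast cannot be informative. That goes too far. The statement in 1.2 is background on TP53-mutated patients in general. Section 3.1 admits patients on flow cytometry or a persistent TP53 mutation alone, and cytogenetics and FISH are repeated pre-study (5.1.A). The plan does not say whether the contrast uses diagnosis or enrollment karyotype. If enrollment, some patients may have cleared their abnormality and the smaller group could exceed 6. Power is modest even with an even split.

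The baseline tables in 15.4.A may make an imbalance visible, but they do not adjust for it.

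**Conclusion.** The point holds as a gap in the analysis of a secondary objective. The plan names two prognostic factors, enrolls widely on both, and compares self-formed groups with no adjusted analysis. Whether this matters depends on imbalance that cannot be known in advance. Under the assumed scenarios, unadjusted rejection is about 9-23% where the group has no conditional effect, against about 5-6% adjusted; with balance it is near 5%. These figures rest on assumed prevalences, hazard ratios and group sizes.

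The cytogenetic contrast is at risk of a near-empty group: about 13-31% power for a hazard ratio of 2 if 2-6 of 60 lack abnormalities, and about 44-56% if 10-15 do. The time point of the karyotype is unstated and largely decides which case applies.

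The change is worth making, but nothing here bears on the primary endpoint.

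**What to change.** In section 15.4.E:

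- Keep the unadjusted tests. Add a prespecified Cox model for OS with age and performance status (0-1 vs 2-3) as covariates, report it beside the unadjusted result, and base any statement about independent association on it.
- Use the same covariates for EFS, and a penalised logistic model for response, only where event or responder numbers allow. The 49 deaths justify an OS model only. The number of responders is unknown, and LFS is not defined in the documents (12.1.B defines relapse-free survival, for CR/CRi patients), so LFS should not be modelled on the strength of that figure.
- Record the performance status grade as an analysis variable. It is assessed for eligibility (3.1) but is not listed in the baseline evaluation (5.1.B) or the study calendar (10.0).
- State whether the cytogenetic contrast uses diagnosis or enrollment karyotype, set a minimum group size, and report the contrast descriptively, without a test, below it. Substituting another split, such as monosomal versus other karyotype, is not clearly better: section 1.2 pools complex and monosomy karyotypes and gives no breakdown.

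The cost is SAP wording, one confirmed data item, a little more analysis and slightly wider intervals. Because adjustment may absorb part of a real association if performance status follows from disease burden, both results should be shown.

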#### **F. Secondary *Molecular Endpoints Analyses***

**Rate of patient specific mutation clearance** after 28, and 56 days of therapy will be determined using an Illumina based platform. We will compare the rate of mutation clearance between the patients who achieve a CR/CRi after 4 cycles and those who do not. We anticipate that we will identify between 6 and 25 exonic SNVs per case (the range obtained with >200 AML samples sequenced to date with whole genome or exome sequencing), and that the expected 95% confidence interval of the mean variant allele frequency will be  $\pm 2.56\%$  and  $\pm 1.25\%$ , respectively, if we assume an anticipated standard deviation of 3.2% within the same clone. The change of tumor burden over time and its association with clinical response will be assessed using 2-way ANOVA for repeated measurement data, followed by the ad-hoc multiple comparisons for between-group differences (e.g., responders vs. non-responders) at given time points as well as the between-time differences within each group. The resultant critical P values will also be corrected using permutation analysis for multiple testing.

The percent decrease in bone marrow methylcytosine will be calculated on day  $10 \pm 1$ . We will compare this reduction with previously published data and between the patients who achieve CR/CRi and those who do not. The correlation of peak plasma levels of decitabine with response will be assessed using 2-sample t-test or Mann-Whitney non-parametric rank-sum test as appropriate. The change of total bone marrow DNA methylcytosine from baseline and its association with both steady-state plasma drug levels and response will be assessed using 2-way ANOVA for repeated measurement data, followed by the ad-hoc multiple comparisons for between-group differences (e.g., responders vs. non-responders) and between-time

differences. Similar analyses will be performed for the correlation of expression profiles and SNP analysis with pharmacokinetic data.

The proportion of patients who achieve mutation clearance to <0.1%, after 3 cycles of decitabine, will be calculated and its 2-sided 90% confidence interval (CI) will also be provided. Using a sensitive sequencing technology such as Haloplex, the sensitivity of PB or BM for detecting residual mutation burden, as well as the *TP53* clonal burden reduction after consolidation with stem cell transplantation will be summarized using contingency tables.

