##### **B. Genome-wide decitabine induced DNA methylation signatures**

To determine whether decitabine treatment results in hypomethylation at consistent CpGs in AML blasts, we will perform whole genome bisulfite sequencing and assess for DNA methylation patterns in pre-treatment (Day 0), at Day 10 (C1D10), at Day 28 (C1D28), and in samples collected at relapse.

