## **F. Correlation of the rate and depth of mutation clearance with survival**

We will assess tumor burden by allele frequency of patient-specific mutations in bone marrow or peripheral blood samples collected pre study, C1D28, C2D28 and C3D28 as well as at regular intervals after transplant. The velocity and depth of tumor response will be correlated to:

- Achievement of clinical CR,
- Time to best response,
- Mutational status,
- Time to disease progression

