14. Typically 28 +/- 4 days. At the discretion of the treating physician this biopsy may be delayed until the next cycle is initiated. The biopsy at the end of cycle 2 will be collected at the discretion of the treating physician.
15. For 2 years
16. Prior negative screening at any time is sufficient. If no prior screening is available, the patient should be tested during screening.
17. If at any bone marrow collection the aspirate is a "dry tap", two additional tubes of blood (10 mL each) will be collected and banked.

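### Section 15.4.F gives serial tumor burden a repeated-measures ANOVA with no rule for missing visits or sample source, so the responder comparison may lose data and be biased in an unknown direction

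*Combined protocol and SAP*

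**What the plan says.** **Model.** Under Section 15.4.F, serial tumor burden and its association with response are to be "assessed using 2-way ANOVA for repeated measurement data, followed by the ad-hoc multiple comparisons for between-group differences". The section names the same ANOVA for methylcytosine: "The change of total bone marrow DNA methylcytosine from baseline and its association with both steady-state plasma drug levels and response will be assessed". It states no missing-visit rule, no sample-source term and no cell-composition term.

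**Visits and groups.** Clearance "after 28, and 56 days of therapy will be determined using an Illumina based platform". The groups are set later: "We will compare the rate of mutation clearance between the patients who achieve a CR/CRi after 4 cycles and those who do not". Section 9.1.F adds a sample at the end of Cycle 3.

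**Where gaps arise.** Note 14 to the Section 10 calendar reads: "The biopsy at the end of cycle 2 will be collected at the discretion of the treating physician". Section 1.3 cites deaths in 15-17% of patients during the first 8 weeks. Section 5.1 takes patients with progression or relapse after two cycles off protocol; Section 5.4 and the Schema word this permissively.

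**Source.** Section 9.1.F measures allele frequency "in bone marrow or peripheral blood samples collected pre study" and at later visits, without saying which source takes precedence. Section 2.3, item 2, treats the relative sensitivity of the two sources as an open question.

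**Methylation target.** Section 9.1.B asks whether treatment "results in hypomethylation at consistent CpGs in AML blasts", whereas the methylcytosine analysis in 15.4.F uses total marrow DNA.

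**The concern.** A classical two-way repeated-measures ANOVA needs a complete row of visits for each patient. Here the losses are foreseeable and partly tied to outcome. A patient who dies in the first 8 weeks has no day-56 sample and, read literally, cannot be in remission after four cycles, so early deaths fall mainly among non-responders. If the remaining non-responders are those who cleared better, their mean clearance looks too good and the contrast with responders shrinks.

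Source adds a second problem. When the Cycle 2 marrow is skipped, or a dry tap leads to extra blood being banked, a patient's series can move from marrow to blood. If the two differ in sensitivity, that move can look like clearance.

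Total marrow methylcytosine has a third. Response requires marrow blasts below 5% (Section 12.1), so after treatment the groups differ in cell mix, and a change in mix can move total methylcytosine without any change within cells.

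**Working it through.** **1. The plan's own figures.** Section 15.4.F gives 95% half-widths for the mean VAF with 6 and 25 variants at SD 3.2%. Half-width = 1.96 × SD / √n:

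- n = 6: 1.96 × 3.2 / √6 = 2.56
- n = 25: 1.96 × 3.2 / √25 = 1.25

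Both reproduce. The clearance powers in 15.4.G also reproduce with a two-sample t-test: 99.8% and 98.6% at SD 3.2, and 91.2% and 82.8% at SD 4.7, against the stated >99%, >98%, 91% and 82%. In all of these n counts variants within a clone. They say nothing about the loss of patients.

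**2. How many day-56 marrows.** Planned enrollment is 60 (15.4.G). Take 16% early deaths, the middle of the cited range, and assume that all occur before the day-56 sample: 60 × 0.84 = 50.4. Marrow uptake is not given. At an assumed 40% to 80%, 50.4 × 0.4 = 20.2 and 50.4 × 0.8 = 40.3, so about 20 to 40 patients. This counts marrow only; blood may still be available.

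**3. What complete cases would show.** All inputs are assumed. Non-responders have a true mean VAF reduction of 5 points at days 28 and 56, SD 15, correlation 0.5 or 0.8. Day 56 is missing in 15%, 30% or 50%, with logistic slope 1.5 on the driver of loss (400,000 simulated patients per setting). The likelihood estimate is

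day-56 mean = complete-case day-56 mean + slope × (all-patient day-28 mean − complete-case day-28 mean).

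| Who is missing at day 56 | Complete cases | Likelihood estimate |
|---|---|---|
| Unrelated to outcome | 5.0 | 5.0 |
| Poor clearance seen at day 28 | 6.3 to 11.3 | 5.0 |
| Poor clearance at day 56, unseen | 7.6 to 13.0 | 6.1 to 11.4 |
| Good clearance at day 28, not re-biopsied | 3.7 down to -1.3 | 5.0 |

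Hand check of row 2 (correlation 0.5, 30% missing): the complete-case means are 9.88 at day 28 and 7.43 at day 56, and 7.43 + 0.5 × (5 − 9.88) = 4.99, against 4.98 simulated.

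**4. Methylcytosine and cell mix.** Let f be the blast fraction and r the blast-to-normal methylcytosine ratio, with no drug effect within cells. Total = f × r + (1 − f). For f falling from 0.60 to 0.05 (assumed):

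- r = 1.1: 1.060 to 1.005, an apparent decrease of 5.2%
- r = 1.0: no change
- r = 0.9: 0.940 to 0.995, an apparent increase of 5.9%

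For f falling only from 0.60 to 0.50 the shifts are a decrease of 0.9% and an increase of 1.1%. The documents give no value of r.

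**The case against.** The plan does not say that incomplete patients are dropped. It names an ANOVA without saying how it is fitted, and comparisons at single time points do not need every visit. That stands: complete-case loss is a property of the classical method and a risk here, not a stated rule.

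The timing also weakens the argument. Section 15.4.F names days 28 and 56, while removal for progression follows two cycles, so it mainly affects the Cycle 3 sample. Patients who progress are also to be sampled at that point. This stands too, but early death and the optional Cycle 2 marrow still bear on day 56.

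The blood list in Section 9.2 does not mark the Cycle 2 sample as optional (the Schema is ambiguous, since it marks marrow and blood together). A skipped marrow therefore need not remove the patient from the VAF analysis. That is right, but keeping the patient then means changing source, which the plan does not handle.

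A reader might infer that non-responder clearance and drug demethylation are overstated. The documents do not support that. The VAF bias reverses if good clearers are the ones not re-biopsied, and the composition shift takes either sign. The planned percent decrease in methylcytosine is at day 10, and nothing in the documents shows a large fall in blasts by then.

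A mixed model is not a cure: it too is biased when loss depends on values never seen. Nor should tumor fraction be a primary adjustment for methylcytosine. It is measured after treatment and lies close to response itself. Blast percentage and founding-clone VAF are not interchangeable either, since the Figure 4 legend in Section 9.1 reports that blast reduction at the end of Cycle 1 does not correlate with clone reduction.

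**Conclusion.** The point holds as one of under-specification with a better method at hand. The named ANOVA, in its classical form, suits a complete and balanced data set, and this schedule is unlikely to yield one. The comparison of clearance between responders and non-responders may lose data and be biased. Overstated non-responder clearance is plausible, but direction and size are unknown. The illustrated range, -1.3 to 13.0 around a true 5, rests entirely on assumed inputs and shows only that the mechanism of loss matters.

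A likelihood model removes the bias when loss depends on observed values. When loss depends on unseen values it reduces the bias in the illustration without removing it. For total marrow methylcytosine, confounding by cell mix is possible in either direction.

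The stakes are limited. Section 2.3 calls the molecular endpoints exploratory, Section 15.4.F calls them secondary, and the primary overall survival analysis does not depend on them.

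**What to change.** In Section 15.4.F:

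1. Replace the ANOVA for tumor burden with a linear mixed model, fitted by likelihood, on log VAF from all available samples. Include visit, response group and their interaction, random effects for patient and for variant within patient, and a fixed effect for source (marrow or blood). State how undetected variants enter the log scale.
2. State that the model assumes data missing at random, and add a sensitivity analysis for loss through death or progression that lets the unseen values be worse than the model predicts.
3. For total marrow methylcytosine, report a sensitivity analysis by marrow blast percentage at the same visit, labelled as such and not used as the primary adjustment.

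The cost is SAP wording. The samples and marrow morphology are already scheduled. The remaining weakness is the missing-at-random assumption, which the second item is there to test.
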